**Adverse events will be analyzed as following:**

1. **Pre-treatment AEs summary:** include pre-treatment AEs from on or after screening date to before date of first IMP.
2. **TEAEs summary up to Week 24 (Treatment Period 1):** TEAEs during the period on or after 1st IMP and up to Week 24 visit or with a start date no more than 140 days after last administration of IMP in case of early treatment discontinuation in part 1.
3. **TEAEs summary from Week 24 onwards (Treatment Period 2):** TEAEs during the period from 1st IMP or rerandomization, that is, 1st IMP or rerandomization  $\leq$  start date of AE  $\leq$  Date of last IMP after re-randomization + 140 days;
4. **Overall TEAEs summary (Overall Treatment Period):** Date of First IMP  $\leq$  start date of AE  $\leq$  Date of last IMP + 140 days;
5. **Post-treatment AEs summary:** include post-treatment AEs that occur  $\geq$ 140 days after last IMP.

The incidence of any AEs, TEAEs and serious TEAEs tables will include only one occurrence of a PT per patient. If a patient reports the same PT multiple times, then that PT will only be incremented by one since patient counts will be presented. As with the PT, if a patient reports multiple AEs within the same SOC, then that SOC will only be incremented by one since patient counts will be presented. For tables showing incidence by SOC, PT and severity, SOC will be sorted Internationally Agreed Order. Within each SOC, PTs will be sorted in descending order of frequency on total of all treatment groups.

All AEs in the clinical trial database will be coded according to MedDRA, which will be used to summarise AEs by primary High Level Group Term (HLGT), High Level Term (HLT), System Organ Class (SOC) and Preferred Term (PT). All AEs, TEAEs and serious TEAEs tables will be displayed in listings.

### 9.1.1 Incidence of Adverse Events

An overall summary of AEs including the counts and percentages of patients will be presented by KY1005 treatment regimen and in the Placebo group for the study periods mentioned in Section 9.1:

- Any AE
- Any SAE
- At least 1 TEAE
- Any related TEAE
- Any severe TEAE
- Any Treatment Emergent SAE
- Any SAE Related to Study Treatment
- Any AE Leading to Treatment Discontinuation
- Any AE Leading to Study Discontinuation
- Any AE Leading to Death
- Any AESI

Below summary tables will be provided by KY1005 treatment regimen and the Placebo group using count and percentages of patients:

- Number (%) of Patients of Pre-treatment Adverse Events by SOC and PT
- Number (%) of Patients with TEAE by SOC and PT from Baseline (Week 0) up to Week 24
- Number (%) of Patients with TEAE by SOC and PT from Week 24 up to Week 68
- Number (%) of Patients with TEAE by SOC and PT from Baseline (Week 0) up to Week 68
- Number (%) of Patients of Post-treatment Adverse Events by SOC and PT
- Number (%) of Patients with TEAE by HLGT, HLT, SOC and PT from Baseline (Week 0) up to Week 24
- Number (%) of Patients with TEAE by HLGT, HLT, SOC and PT from Week 24 up to Week 68
- Number (%) of Patients with TEAE by HLGT, HLT, SOC and PT from Baseline (Week 0) up to Week 68
- SOC Number (%) of Patients of TEAEs by PT from Baseline (Week 0) up to Week 24
- Number (%) of Patients of TEAEs by PT from Week 24 up to Week 68
- Number (%) of Patients of TEAEs by PT with total incidence  $\geq 5\%$  from Baseline (Week 0) up to Week 24
- Number (%) of Patients of TEAEs by PT with total incidence  $\geq 5\%$  from Week 24 up to Week 68
- Number (%) of Patients of TEAEs by PT with total incidence  $\geq 5\%$  from Baseline (Week 0) up to Week 68
- Number (%) of Patients of TEAEs by PT with total incidence from Baseline (Week 0) up to Week 24
- Number (%) of Patients of TEAEs by PT with total incidence from Week 24 up to Week 68

- Number (%) of Patients of TEAEs by PT with total incidence from Baseline (Week 0) up to Week 68
- Incidence Rate per Patient Year Exposed from Baseline (Week 0) up to Week 24
- Incidence Rate per Patient Year Exposed from Week 24 up to Week 68
- Incidence Rate per Patient Year Exposed from Baseline (Week 0) up to Week 68

All AEs and TEAEs will be presented in a listing.

A separate listing will be presented for Pre-treatment AEs (with details of Severity, Seriousness, first dose date, last dose date, if leading to study discontinuation, if leading to death, relative day of AE) and Post-treatment AEs (with details of Severity, Seriousness, first dose date, last dose date, if leading to study discontinuation, if leading to death, relative day of AE) .

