### 2.3. Exploratory Objectives and Endpoints

## 3. Investigational Plan

### 3.1. Overall Study Design and Plan

This is a Phase IIb, randomised, double-blind, placebo-controlled, parallel group, multicentre dose ranging study to characterise the efficacy and safety of SC administered KY1005 in adult patients with moderate-to-severe AD who have a documented history, within 6 months prior to Baseline, of an inadequate response to, or inadvisability of, topical treatments.

Patients who continue to meet the eligibility criteria at Baseline will be randomised 1:1:1:1:1 to receive a SC dose of KY1005, or matching Placebo. The randomisation will be stratified by disease severity (moderate/ severe) and region at baseline. Disease Severity at baseline is defined as moderate (Baseline EASI  $\leq$  21) and severe (Baseline EASI  $>$ 21). Up to 350 patients (approximately 70 patients per treatment arm) will be enrolled.

Four different SC KY1005 dosing regimens will be tested versus Placebo. From Baseline up to Day 169 (Week 24), investigational medicinal product (IMP) will be administered at the following doses and intervals; 500 mg loading dose (given as [redacted] SC administration) followed 28 days later and thereafter with 250 mg every 4 weeks (Q4W) or the following regimens from Baseline: 250 mg Q4W, or 125 mg Q4W or 62.5 mg Q4W or Placebo Q4W.

At Baseline those patients not receiving a KY1005 loading dose will receive both KY1005 and Placebo to maintain the study blind. All patients will therefore receive [REDACTED] SC doses at Baseline.

To enable Placebo patients and those patients randomised to the KY1005 62.5 mg Q4W, 125 mg Q4W and 250mg Q4W treatment arms to receive KY1005 at a dose expected to elicit a meaningful clinical response (based on prior clinical evidence), patients who do not achieve  $\geq$  EASI 75 or IGA 0/1 at Week 24 will be invited to enroll in the LTE study (LTS17367) where they will receive KY1005.

[figure not shown]

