In those patients who achieve  $\geq$  EASI 75 or who attain IGA 0/1 at Week 24, a re-randomisation will occur pre-dose at Day 169 (Week 24) and patients will enter the second study period. The week 24 randomisation will be stratified by IGA response (IGA 0/1 or IGA 2/3/4) at week 24. This will occur irrespective of whichever dose group the patient was randomised to at Baseline including Placebo. Patients will be randomised in a 3:1 manner to be withdrawn from therapy or to continue their pre-Week 24 dose/interval. To maintain the blind, those patients randomised to the withdrawal arm will receive Placebo Q4W. [REDACTED]

At Day 365 (Week 52), patients who have completed the post-Week 24 period and have not experienced loss of clinical response will have an additional 112 days' safety follow-up up to Day 477 (Week 68) and then be discharged from the study. The last dose will be given no later than Day 337 (Week 48) and as such safety follow-up will be 140 days following last dose of IMP. [REDACTED]

The duration of the study will be up to 28 days for screening and then up to approximately Day 477 (Week 68) (to Day 365 [Week 52] plus 112 days safety follow-up, [REDACTED] for all patients unless enrolled into the LTE study (LTS17367) at Day 169 (Week 24) or due to loss of clinical response at or after Day 197 (Week 28). The last dose will be given no later than Day 337 (Week 48).

The IMPs are KY1005 (SAR445229), hereby known as KY1005, or matching Placebo.

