##### For Part 2:

The data in Part 2 will be presented according to treatment sequence planned or received. These analyses include the following: drug exposure, prior/concomitant medications for AD and non-AD, rescue and prohibited medications and procedures impacting efficacy, rescue medications, prohibited medications and procedures, concomitant procedures, adverse events, injection site reactions, efficacy parameters (EASI, IGA, NRS etc), 12-lead electrocardiogram parameters, laboratory parameters, PK parameters, and ADA. Patient disposition, demographics and baseline characteristics, significant protocol deviations, and medical history will be presented among patients enrolled in Part 2. Data on some endpoints such as prior/concomitant medications for AD and non-AD, rescue and prohibited medications and procedures impacting efficacy, rescue medications, prohibited medications and procedures, concomitant procedures, efficacy adverse events, laboratory parameters, PK and ADA will be presented from baseline up to Week 52 or Week 68 among patients enrolled in Part 2. In addition, presentation of rescue and prohibited medications and procedures will also be done for Week 52 to Week 68 data only.

All CIs presented will be 95% (two-sided) CIs.

Non-zero percentages will be rounded to one decimal place. When count data are presented, percentages will be rounded to one decimal place. If count is 0, the percentage will not be presented. CI will be presented to two decimal places for proportion, wherever applicable. A row denoted "Missing" will be included in count tabulations where specified on the shells to account for dropouts and missing values.

The denominator for all percentages will be the number of patients with non-missing values of corresponding parameter in that treatment within the analysis population of interest, unless otherwise specified.

For the summary statistics of all numerical variables, unless otherwise specified, minimum and maximum will be displayed to the same level of precision as reported up to a maximum of three decimal places. Mean and median will be displayed to one level of precision greater than the data collected up to a maximum of three decimal places. Standard deviation / standard error will be

displayed to two levels of precision greater than the data collected up to a maximum of three decimal places.

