#### 4.3.1. All Enrolled Set

All Enrolled Analysis Set includes all patients who signed an informed consent form with no screen failures. Analysis will be based on treatment allocated at randomisation.

#### 4.3.2. Full Analysis Set for Part 1

The Full Analysis Set (FAS1) for Part 1 includes all randomised patients up to week 24. Efficacy analysis will be based on treatment allocated at randomisation.

#### 4.3.3. Full Analysis Set for Part 2

The Full Analysis Set (FAS2) for Part 2 includes all re-randomised patients at Week 24 up to week 52. Efficacy analysis will be based on treatment allocated at re-randomisation.

#### 4.3.4. Safety Analysis Set for Part 1

The safety set (SAF1) for Part 1 will consist of all patients who take at least one dose of study treatment, including Placebo up to week 24. Any analysis based on the SAF1 will be based on the treatment actually received, regardless of assigned treatment according to the planned randomisation.

#### 4.3.5. Safety Analysis Set for Part 2

The safety set (SAF2) for Part 2 will consist of all re-randomised patients at Week 24 who take at least one dose of study treatment on or after Week 24. Any analysis based on the SAF2 will be based on the treatment actually received at week 24, regardless of assigned treatment according to the planned randomisation.

#### 4.3.6. Pharmacokinetic Set for Part 1

The PK set will consist of all randomized patients in the SAF1 with at least one post-Baseline PK sample (with adequate documentation of dosing and sampling dates and times) up to week 24. Any analysis based on the PK1 will be based on the treatment actually received, regardless of assigned

treatment according to the planned randomisation. Patients who received only placebo will not be included.

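### The common adverse-event tables appear to apply a 5% cut to all arms pooled, so an event raised in a single dose will usually miss them unless the excess is large or the background is near 5%

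*SAP*

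**What the plan says.** Among the adverse-event summaries in SAP 9.1.1 are three limited to preferred terms whose total incidence is 5% or more, one for each of Weeks 0-24, 24-68 and 0-68: "Number (%) of Patients of TEAEs by PT with total incidence". Three further tables in the same list carry the phrase total incidence with no threshold. The term is not defined. The closest guide is the sorting rule in SAP 9.1, under which "PTs will be sorted in descending order of frequency on total of all treatment groups".

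The design is in SAP 3.1. Patients are "randomised 1:1:1:1:1 to receive a SC dose of KY1005, or matching Placebo", and "Up to 350 patients (approximately 70 patients per treatment arm) will be enrolled". At Week 24, responders from every arm are re-randomised: "Patients will be randomised in a 3:1 manner to be withdrawn from therapy or to continue their pre-Week 24 dose/interval". Placebo responders are included: "This will occur irrespective of whichever dose group the patient was randomised to at Baseline including Placebo". The Part 2 safety set (SAP 4.3.5) "will consist of all re-randomised patients at Week 24 who take at least one dose of study treatment on or after Week 24". For display, "The data in Part 2 will be presented according to treatment sequence planned or received".

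SAP 9.1.1 also plans tables by regimen without any threshold: by SOC and PT, and by HLGT, HLT, SOC and PT, for all three periods, and by PT alone for the first two. All AEs and TEAEs are listed.

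**The concern.** This is a dose-ranging trial whose stated aim includes describing safety across a range of doses (SAP Section 1). The safety pattern that matters for comparing doses is one regimen differing from the others. A cut applied to the pooled rate averages that regimen with four arms that do not share the excess, so the event can fall below 5% overall while well above 5% in the arm concerned.

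The effect is stronger in Part 2. The groups that continue active drug have the longest exposure, but each is a small part of the re-randomised set, three quarters of which has been switched to placebo injections. At stake is which events are presented as common, and so whether a dose-specific signal is visible in the summary table or only in the full ones.

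**Working it through.** **Inputs.** 350 patients, 70 per arm, five equal arms (SAP 3.1). Re-randomisation 3:1, so one quarter of each arm's responders continue (SAP 3.1). Protocol 3.6 assumes 30% dropout to Week 24 and 49 completers per arm. These figures reproduce: 5 × 70 = 350 and 70 × (1 − 0.30) = 49. The documents state no figure derived from the 5% rule. They also give no Week 24 responder rates for this trial, so those are assumed below over a range. The pooled reading of total incidence is an inference.

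**Part 1, rate needed.** 0.05 × 350 = 17.5, so 18 patients are needed. If all are in one arm, 18/70 = 25.7%. With rate b in each of the other four arms, (x + 4b)/5 ≥ 0.05 gives x ≥ 0.25 − 4b:

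| Rate in each other arm | Rate needed in the one arm |
|---|---|
| 1% | 21% |
| 2% | 17% |
| 3% | 13% |
| 4% | 9% |

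**Part 1, chance of being listed.** Let X ~ Bin(70, a) in the affected arm and Y ~ Bin(280, b) in the other four combined. The pooled rule lists the event if X + Y ≥ 18. An any-arm rule needs 0.05 × 70 = 3.5, so 4 of 70 (5.7%) in at least one arm.

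| One arm | Each other arm | Pooled rule | Any-arm rule |
|---|---|---|---|
| 10% | 2% | 8% | 94% |
| 12% | 2% | 16% | 98% |
| 12% | 3% | 42% | 99% |
| 12% | 4% | 68% | 99% |
| 15% | 2% | 34% | over 99% |

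**Part 2, one continuing dose.** With responder rate r in an arm and S the sum of r over the five arms, its share of the re-randomised set is 0.25 × r/S. An event confined to that group needs a rate of 0.05 divided by the share.

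- Equal responders in all five arms: share 0.25 × 0.20 = 5.0%; needed 100%.
- Phase 2a Week 16 EASI 75 rates (Protocol Table 1-1; 30/54 on active, both doses pooled, and 6/24 on placebo): S = 4 × 0.556 + 0.25 = 2.472; share 5.6%; needed 89%.
- No placebo responders, active arms equal: share 0.25 × 0.25 = 6.25%; needed 80%.
- Doses differing, assumed 70/60/50/40% on active and 20% on placebo: S = 2.4; needed 69% in the arm with most responders and 120% in the active arm with fewest, where the event could not be listed at all.

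**Part 2, one withdrawal group.** The share is 0.75 × r/S. Needed: 33% with equal responders, 30% on the Phase 2a rates, 27% with no placebo responders.

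**Part 2 with a background.** With equal responders and rate b in the other 95% of patients, the continuing group needs (0.05 − 0.95b)/0.05: 81% at b = 1%, 62% at 2%, 43% at 3%, 24% at 4%.

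**Price of an any-arm rule in Part 1.** For an event at the same true rate in all five arms:

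| Uniform rate | Pooled rule lists it | Any-arm rule lists it |
|---|---|---|
| 2% | 0.03% | 23% |
| 3% | 2% | 58% |
| 4% | 17% | 84% |

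**The case against.** The strongest reply is that nothing is hidden. The same section plans unfiltered tables by regimen and full listings, and SAP 9.1.2 to 9.1.7 add tables by regimen for serious events, relationship, severity, discontinuation, death and AESIs. Counts by arm in a filtered table are correct; only the selection of terms is affected. No test, estimand or decision rule uses these tables. All of this stands, and it limits the point to presentation.

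It can also be said that the pooled reading is not established, since the sorting rule was not written to define the 5% cut. That is fair. But the term is then undefined in a rule that decides what is shown, and three neighbouring tables use it with no threshold at all.

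An any-arm rule also admits noise, as the last table in the working shows. That is a real cost.

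Three stronger readings are tempting and are not supported. A reader might infer that an event raised in one dose is always left out; at 12% in one arm it is listed in 42% of trials with a 3% background and 68% with 4%. A reader might infer that in Part 2 every patient on a continuing dose must have the event; that is exact only with equal responder numbers in all five arms and no such event elsewhere. And a reader might take the twenty-fold dilution of a continuing group (a 5% share) as true of Part 2 generally; a withdrawal group is 15% of the set with equal responders, a dilution of about 6.7-fold.

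**Conclusion.** The point holds as a cheap improvement to how safety is presented. If total incidence means all arms pooled, the three filtered tables suit a five-arm dose comparison poorly. In Part 1 a six-fold excess in one dose (12% against 2%) would be missing from the table in about 84% of trials. In Part 2 the rate needed for an event confined to one continuing dose is roughly 70-100%, and beyond reach in an arm with few responders; for a withdrawal group it is about 27-33% when doses respond alike.

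The Part 1 figures rest on 70 per arm and the pooled reading. The Part 2 figures also rest on assumed responder rates. The Phase 2a rates are only a guide, being Week 16 EASI 75, whereas re-randomisation is at Week 24 on EASI 75 or IGA 0/1. The size of the problem shrinks as the background approaches 5%. The documents do not support any claim that safety data are lost or that the by-arm counts are wrong.

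**What to change.** Define total incidence in SAP 9.1.1, including for the three tables that carry no threshold. Then:

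- For Weeks 0-24 and 0-68, select preferred terms with an incidence of at least 5% in any treatment group.
- For Weeks 24-68, select terms with at least two patients and at least 5% in any re-randomised group.

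The floor of two is needed because a continuing group is likely to hold about 6-10 patients (0.25 × 0.5 × 49 = 6.1; 0.25 × 0.593 × 70 = 10.4), so one patient is already 10-17%. The count of two is in effect the binding rule: the 5% cut asks for more than two patients only in groups larger than 40 (2/40 = 5%). If the Week 0-68 table is shown by Part 2 sequence, as SAP Section 4 foresees for some outputs, the same floor belongs there.

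The cost is one line in the SAP and a change to the table shells. The tables become longer and list more chance events. A footnote giving the selection rule would help readers allow for that. No data collection, test or clinical rule changes.

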### 9.1.2. Serious Adverse Events

Below summary tables will be provided by KY1005 treatment regimen and the Placebo group using count and percentages of patients for all study periods mentioned in Section 9.1:

- Number (%) of Patients with Serious TEAEs by SOC and PT from Baseline (Week 0) up to Week 24
- Number (%) of Patients with Serious TEAEs by SOC and PT from Week 24 up to Week 68
- Number (%) of Patients with Serious TEAEs by SOC and PT from Baseline (Week 0) up to Week 68

All SAEs will be presented in a listing.

A listing of SAEs for screen failures will be presented.

### 9.1.3 Relationship of Adverse Events to Study Drug

Below summary tables will be provided by KY1005 treatment regimen and in the Placebo group using count and percentages of patients:

- Number (%) of Patients with TEAEs by SOC, PT and Relationship from Baseline (Week 0) up to Week 24
- Number (%) of Patients with TEAEs by SOC, PT and Relationship from Week 24 up to Week 68
- Number (%) of Patients with TEAEs by SOC, PT and Relationship from Baseline (Week 0) up to Week 68

The relationships will be collected as the possibility that study drug caused the event i.e. the relationships are “Not Related”, “Related”.

### 9.1.4. Severity of Adverse Event

The severity of the AE will be graded based on the Common Terminology Criteria for Adverse Events (CTCAE) as Grade 1, Grade 2, Grade 3. In the TEAE severity table, if a patient reported multiple occurrences of the same AE, only the most severe AE will be presented. AEs with missing severity will be presented on tables as “Unknown” but will be presented in the data listing with a missing severity.

Adverse events will be classified by the Investigator according to the following criteria:

- Mild (Grade 1 Common Terminology Criteria for Adverse Events [CTCAE]): Asymptomatic or mild symptoms; clinical or diagnostic observations only; intervention not indicated.
- Moderate (Grade 2 CTCAE): Minimal, local or noninvasive intervention indicated; limiting age-appropriate instrumental Activities of Daily Living (ADL). Instrumental ADL refers to preparing meals, shopping for groceries or clothes, using the telephone, managing money, etc.
- Severe ( $\geq$  Grade 3 CTCAE): Severe or medically significant but not immediately life-threatening; hospitalization or prolongation of hospitalization indicated; disabling, limiting self care ADL. Self care ADL refers to bathing, dressing and undressing, feeding self, using the toilet, taking medications, and not bedridden. Life-threatening consequences; urgent intervention indicated; Death related to AE.

Changes in the severity of an AE should be documented to allow an assessment of the duration of the event at each level of severity to be performed. Adverse events characterized as intermittent require documentation of onset and duration of each episode.

Below summary tables will be provided by KY1005 treatment regimen and in the Placebo group using count and percentages of patients:

- Number (%) of Patients with TEAEs by SOC, PT and Severity from Baseline (Week 0) up to Week 24
- Number (%) of Patients with TEAEs by SOC, PT and Severity from Week 24 up to Week 68
- Number (%) of Patients with TEAEs by SOC, PT and Severity from Baseline (Week 0) up to Week 68

